Database protection: Participant usage of the Meditation Coach app will be accessed through the app's dashboard, VA App Connect, which only investigators of the study will be able to access. This will allow us to generate invitation codes so that participants assigned to the MM condition will be able to use the research version of the Mindfulness Coach app and will allow us to download data for users (real-time access) in JSON files. We will use SAS code to extract the data. This data will be stored on our institutions' secured drive. The statistician from UTHealth will be provided access to these files per the institutional access policy. The password-protected deidentified files will be shared among investigators. Data will be stored on secure UTHealth desktops that can only be accessed using an institutional ID and password. A separate linking log with identifiable information will be stored on the institution's secured server. The RedCap survey results and reports are stored on UTHealth RedCap secure servers. A UTHealth email account is needed to log in. Excel spreadsheets used to tabulate and analyze data will be password protected and stored on protected UTHealth desktop computers located in locked project offices. As all data will be collected online (RedCap) or via phone interview and entered directly into RedCap by the research coordinator. Thus, we do not anticipate any usage or storage of any paper documents in this proposed study.

Quality control and assurance

Data quality and management: The investigators and study staff will review all data collection forms on an ongoing basis for data completeness and accuracy as well as protocol compliance. All data except the pain measure will be completed via RedCap by the participants. The pain measure will be collected via phone interview with a research assistant (RA), as this measure is not validated for collection via self-report. The RA will enter this data directly into RedCap during the phone interview. Additionally, while creating RedCap surveys to collect outcome data, we will restrict the entry of specific variables to prevent data entry errors. For example, the minimum age entry will be restricted to 18 per study inclusion criteria (participants' age will have already been verified as over 18 by the RC during the screening phone interview). The survey was carefully designed and tested multiple times to identify any potential issues with data collection with the input from Community Advisory Board. Additionally, we will audit the data for the first two months bi-weekly and then quarterly during the study period to prevent systematic errors.

Publication Plan

We acknowledge the importance of the timely release of scientific information and resources to the broader community. We are also aware of the policies and guidelines established by the NIH regarding the release of research results. Therefore, we plan to present the results generated by these studies at national and international conferences and publish the data in peer-reviewed journals in a timely fashion.

ATTACHMENTS

1. Updated Assessments (RedCap survey)
2. Updated Consent Document
3. Updated screening telephone script
4. Updated MM orientation tutorial slides
5. Updated TED talk orientation tutorial slides
6. Updated flyer

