Our multidisciplinary, interinstitutional team of investigators proposes to randomize 60 SCI patients experiencing chronic pain to practice audio-guided MM for **≥ 10 minutes daily for 6 weeks** using the free app “Mindfulness Coach” developed by the Department of Veteran Affairs, or to view health and wellness-related TED talks for **≥ 10 minutes daily for 6 weeks** on the free TED app (active control). Primary outcomes are the **feasibility and acceptability** of proposed interventions in people with SCI and chronic pain. Secondary outcomes include the feasibility of collecting patient-reported outcomes of pain, anxiety, depression, mindfulness, quality of life, stress, fatigue and sleep disturbance.

Given the great need for remotely delivered, low-cost chronic pain management and unique physiological limitations among persons with SCI, it is essential to determine the **feasibility** and **acceptability** of a free, publicly available app-based MM intervention prior to conducting a larger efficacy study. With the emerging use of telemedicine in this COVID-19 era, therapy-focused apps, and remote data collection are becoming increas  IRB NUMBER: HSG-MS-22-0035 making this line of inquiry

both **timely and innovative**. Furthermore, the app-guided MM intervention ha

IRB APPROVAL DATE: 02/27/2024
tial to facilitate self-

management of pain by persons with SCI, as the MM exercises can be practiced at the individual's preferred time and place. *The long-term goal* of this study is to improve pain management and QOL of people with SCI living with chronic pain by identifying affordable and accessible app-guided interventions which can be used as an adjuvant tool after SCI in conjunction with other treatments.

Background Information

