In all of these recruitment activities, we will share our study announcement and/or recruitment flyer and invite those interested to contact the project research coordinator (RC) by email or phone for additional information and/or to schedule a screening interview. Additionally, the recruitment flyer will contain a QR code, which will open a survey that will ask the participant to enter their phone number and email address so that the research coordinator may contact them. The RC will follow up with interested individuals by phone and conduct an initial eligibility screening (i.e., whether they meet the inclusion and exclusion criteria). For eligible individuals, the RC will email them a link to an online informed consent form (via REDCap), review informed consent with the study candidate over the phone, and answer any questions. The RC will then ask individuals to provide written online consent, using a mouse or stylus, in the signature box of the online consent form. The RC will email a copy of the consent form to individuals who provide consent for their personal records. All screening, enrollment, and consent materials and procedures will be reviewed with our community advisors prior to implementation to ensure they are easy to understand and are optimally accessible. For eligible individuals who do not consent to the study, the RC will inquire about and document the reason for refusal and thank them for their time.

Baseline assessment: After consent is obtained, the RC will text and email a RedCap link to complete a 30-minute baseline assessment survey. All measures listed in the Measure section of the proposal will be collected via RedCap except the **International SCI pain basic data subset⁹⁶ (ISPBD version 2)** questionnaire. This measure is not validated for data collection by survey link and requires administration by a trained professional. Hence, this measure will be administered by the study personnel via phone interview or video conference  trained to administer the ISPBD by the PI ([name]). Participants who do not complete the survey imme 

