followed a phone call (if needed) to assess if the participant experiencing any barriers to completing the survey. In addition to collecting outcome measures (see measures section), we will also collect information on demographic and disability characteristics including age, sex, gender, education level, employment status, marital status, etiology of injury, year of injury, level of injury, and completeness of injury.

Randomization: After completing the baseline assessment, eligible participants will be randomized in a 1:1 ratio to the mindfulness meditation (MM) or health education (HE) (active control) condition using the permuted blocks randomization with varying block sizes. We will stratify based on sex; thus, a random assignment will be conducted separately for men and women to ensure that women and men have comparable representation in the two conditions. Given literature suggesting sex-dependent differences, in pain and recovery from SCI, this randomization strategy reduces the risk that unequal sex distribution will potentially confound feasibility and acceptability ratings. It will also help us evaluate potential sex-related differences in adherence or satisfaction ratings in the two conditions.

Intervention: After randomization, the RC will schedule a 30-minute training session with the participant using Zoom. This one-on-one videoconference will describe their assigned condition (MM or HE), provide guidance on how to engage in the respective condition (i.e., how to download and use respective apps), and instruct participants on the frequency of engagement expected during the 6-week intervention period. We will develop a checklist of training components to ensure consistency in the delivery of the training by the RC.

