Aim 1. To assess the **feasibility of participating** in a 6-week app-guided MM intervention (daily sessions of \geq 10 minutes 6 days/week) and HE condition (viewing daily health education-related TED Talks of \geq 10 minutes 6 days/week) in people with SCI who have chronic pain, we will collect the: a) **recruitment rate**: the proportion of eligible people who provide consent, b) **adherence rate**: the proportion of participants in each group who complete the minimum recommended minutes (i.e., 60 minutes/per week) of using the MM or HE app during the 6 weeks intervention, and c) **retention rate**: the proportion of participants in MM and HE conditions who meet our criteria for adherence and complete the baseline, immediate post-intervention and 6-week follow-up assessments.

Aim 2. To examine the **acceptability of participating** in a 6-week app-guided MM intervention (daily sessions of \geq 10 minutes 6 days/week) and HE condition (active control), we will collect quantitative and qualitative patient-reported satisfaction with their video-conference training, their assigned app, and their assigned practice sessions. Quantitative satisfaction will be assessed using a program evaluation questionnaire that will assess their satisfaction with the app. This measure also allows participants to provide open-ended comments and suggestions. Additionally, the post-treatment assessment will contain open-ended questions to assess barriers to adherence, to inform strategies and to enhance compliance with the sessions in future studies.

Aim 3. To examine the **feasibility and acceptability of data collection procedures**, we will collect patient-reported measures of pain, depression, anxiety, mindfulness, and QOL and calculate the **proportion of participants in MM and HE conditions who complete the baseline, the immediate post-intervention, and the 6-week follow-up assessments**. IRR NUMBER: HSC-MS-22-0035 IRR APPROVAL DATE: 02/27/2024

follow-up assessments. Collecting these patient-reported outcomes will be determined to be feasible and acceptable if at least 70% of participants complete ≥ 70% of the assessment items.

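### The Aim 3 completion proportion counts only participants already in a study condition, so its baseline component is met by construction and says nothing about whether baseline data collection is feasible.

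*Combined protocol and SAP*

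**What the plan says.** The order of events is set out under Study Procedures. Baseline follows consent: "After consent is obtained, the RC will text and email a RedCap link to complete a 30-minute baseline assessment survey". A staff-administered pain interview is part of the same assessment. For people slow to respond, the section provides for a telephone call, if needed, to "assess if the participant experiencing any barriers to completing the survey". Allocation comes next: "After completing the baseline assessment, eligible participants will be randomized in a 1:1 ratio".

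The Measures section, Aim 3, says "we will collect patient-reported measures of pain, depression, anxiety, mindfulness, and QOL" and reports the "proportion of participants in MM and HE conditions who complete the baseline, the immediate post-intervention, and the 6-week follow-up assessments". Data collection is then judged feasible and acceptable "if at least 70% of participants complete ≥ 70% of the assessment items". The Objectives and the Analysis Plan (Aim 3) add a response rate per measure at each of the three time points and name no denominator.

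Under Aim 1, recruitment is "the proportion of eligible people who provide consent". Retention is counted among MM and HE participants who are adherent and complete the assessments. The Analysis Plan (Aim 1) also promises month-by-month numbers at screening, consent and randomisation, and a CONSORT diagram.

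**The concern.** A feasibility rate is informative only if it can come out low. Here the population is defined by having passed the step that the rate is meant to assess. The 30-minute survey and the pain interview come before randomisation, and anyone who stops there is never in MM or HE.

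The Measures section makes later use of these instruments as primary outcomes depend partly on whether completing them proves feasible. A later trial with the same battery before randomisation would need to know what share of consenting people reach allocation. The stated proportion cannot tell them, and the Aim 1 rates do not fill the gap: recruitment stops at consent, and retention starts from allocated participants.

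**Working it through.** **The plan's own figures.** The Sample size paragraph gives margins of error for n = 30 per arm. The half-width is 1.96 × √(p(1−p)/n).
- p = 0.50: 1.96 × √(0.25/30) = 17.9%
- p = 0.75: 1.96 × √(0.1875/30) = 15.5%

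Both agree with the plan. They concern precision among randomised participants and do not bear on who belongs in the denominator.

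**Logic of the definition.** Let C be those who consent, B those who complete baseline and R those randomised. Under Study Procedures, R lies within B and B lies within C. The Aim 3 proportion is taken over R.
- Read as three separate rates, the baseline rate is (number in both B and R)/(number in R) = 1.
- Read as one joint rate, requiring baseline as well as both later assessments removes nobody from R. The result is the same as requiring the two later assessments alone.

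On either reading the baseline condition adds no information at assessment level. Completing baseline is not defined item by item, so item-level completeness within R can still be below 100%.

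**Where the people in C but not in R appear.**
- Aim 1 recruitment: counted as successes, because they consented.
- Aim 1 retention: absent, because it counts MM and HE participants.
- Aim 3 completion proportion: absent, for the same reason.
- 70%/70% rule: not stated; it says only participants.
- Per-measure response rates: not stated.
- Monthly counts and CONSORT diagram: recoverable as consented minus randomised.

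**Illustration.** The documents do not give the number consented but not randomised, so it is assumed. All of the loss is taken to be baseline non-completion. The randomised total is 60, from General Information ("proposes to randomize 60 SCI patients experiencing chronic pain"). Baseline completion = 60/(60 + number lost), with Wilson 95% intervals.

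| Consented (assumed) | Lost | Completion among consented | Stated Aim 3 definition |
|---|---|---|---|
| 63 | 3 | 60/63 = 95.2% (86.9 to 98.4%) | 60/60 = 100% (94.0 to 100%) |
| 66 | 6 | 60/66 = 90.9% (81.6 to 95.8%) | 60/60 = 100% (94.0 to 100%) |
| 75 | 15 | 60/75 = 80.0% (69.6 to 87.5%) | 60/60 = 100% (94.0 to 100%) |

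The last column does not change however many people are lost.

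**The case against.** The strongest reply is that little is really lost. The Analysis Plan already commits to counts at consent and at randomisation and to a CONSORT diagram with reasons, so a reader can form the ratio. That stands, and it is the main reason the point is minor. Those counts sit under Aim 1, however, and are tied neither to the Aim 3 rate nor to its criterion.

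A reader might infer that non-finishers can never enter any Aim 3 rate. The documents do not support that. The 70%/70% rule and the per-measure response rates name no restricted population, and the protocol uses the word participants for people who have not yet been randomised. Only the completion proportion excludes them in terms.

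A reader might also infer that the 70%/70% rule is passed automatically at baseline. That does not follow either, because the rule works on items and complete baseline is not defined at item level.

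Nor should the telephone call be read as a forecast of substantial loss. It is a contingent reminder step, and part of the surrounding text is missing from the extracted document.

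Finally, the illustration attributes every loss to baseline non-completion. Some people may withdraw for other reasons or be found ineligible, since it is eligible participants who are randomised. The Sample size paragraph also speaks of enrolling 60 without saying at which step enrolment is counted. These are fair limits on the figures, but they leave the logic of the denominator untouched.

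**Conclusion.** The concern holds in a limited form. One of the three Aim 3 descriptions, the completion proportion, has a stated denominator that makes its baseline component about 100% at assessment level, so it gives no evidence on the feasibility of baseline collection. The other two leave the denominator open.

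The true size is unknown. For assumed losses of 3 to 15 people against 60 randomised, completion among the consented would be 95% to 80%, while the stated definition would show 100%. Randomised participants remain the right denominator at post-intervention and at 6 weeks. Severity is minor: the aim is secondary and descriptive, no hypothesis test depends on it, and the loss can be reconstructed from planned counts.

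**What to change.** In Aim 3, in both the Measures section and the Analysis Plan:

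1. Calculate baseline completion (survey and pain interview) and the per-measure baseline response rates among all consented participants, with a 95% confidence interval. Report them overall only, since people who do not finish baseline have no arm. Show separately those found ineligible after consent or withdrawn for other reasons.
2. Apply the 70%/70% rule at each assessment, with all consented participants as the denominator at baseline and all randomised participants at post-intervention and at 6 weeks. Count people who do not return an assessment as not complete.

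The cost is a few sentences and some extra tabulations of data already held. The baseline figure will look less favourable than 100%, and the criterion becomes somewhat harder to meet because it is judged three times and non-returners count against it.

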Aim 2. To examine the acceptability of a 6-week app-guided MM intervention and HE condition in people with SCI who have chronic pain. To achieve this aim, we will measure participant-reported satisfaction with the initial training to orient them to their randomly assigned condition and their satisfaction with the assigned home practice sessions at the end of 6 weeks (post-intervention).

Aim 3. To examine the feasibility of data collection procedures. We will collect measures of mindfulness, pain, anxiety, depression, and QOL and calculate the response rate for each measure at baseline, immediate post-intervention, and 6-week follow-up to evaluate the feasibility and acceptability of collecting these data.

Study Design

IRB NUMBER: HSC-MS-22-0035
IRB APPROVAL DATE: 02/27/2024

An RCT design will be used to evaluate the feasibility and acceptability of a 6-week app-based mindfulness meditation (MM) intervention (Table 1) and health education (HE; active control) condition in people with SCI who have chronic pain.

Study Population

Participants: We will screen potential participants using the following inclusion/exclusion criteria.

Inclusion Criteria: 1) At least 18 years of age, 2) Traumatic SCI of at least 6 months duration, 3) Chronic pain [defined as pain lasting at least 3 months with a pain intensity rating of 4 or higher on a 10-point visual analog scale], and 4) Understand spoken and written English sufficiently to provide informed consent, participate in the intervention and complete study surveys

Exclusion Criteria: 1) Lack of daily access to the internet using a smartphone or smart tablet, 2) Cognitive impairment (determined by their inability to demonstrate comprehension of informed consent by correctly answering 4 out of 5 questions pertaining to the study), 3) Significant visual/hearing impairment that does not allow the use of the MM and/or HE apps' audiovisual presentations, 4) Use of any kind of meditation more than once a week in the last 3 months, 5) Inability to provide or obtain an email address for communication with study staff, and 6) Inability to operate the app download or study related survey using a smartphone.

Study Procedures

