The following patient reported outcomes will be collected at baseline and the immediate post-treatment and 6-week post-treatment follow up. These measures are included in this pilot trial to determine the feasibility and acceptability of collecting this data. If this pilot trial reveals that participation in the intervention and completion of these measures are feasible and acceptable, these measures will serve as primary outcome measures in a subsequent effectiveness trial.

Pain will be assessed using the **International SCI pain basic data subset⁹⁶ (version 2)**. This pain measure is one of the CDEs recommended by the National Institute of Neurological Disorders and Stroke (NINDS) for measurement of pain in people with spinal cord injury. This measure collects information on the interference of pain with daily activities, mood and sleep. It also evaluates location, type of pain, the intensity of pain, duration of pain and treatment of pain for 3 worst pain problems reported by a person with SCI.

Pain-related distress will be assessed using the **Chronic Pain Acceptance Questionnaire (CPAQ-R8)**, which consists of 8 items assessing acceptance of pain rated on a 0 (never true) to 6 (always true) scale to generate scores on two subscales: activity engagement and pain willingness. The CPAQ has been validated in patients with chronic pain.¹⁰⁷

Brief Pain Catastrophizing Scale (Brief PCS) measures three aspects of catastrophic cognitions about pain-rumination, magnification, and helplessness. Each question has five response options ranging from 0 (not at all) to 4 (all the time) scale.

Depression will be measured by the eight-item **Patient Health Questionnaire (PHQ-8)**,^{108 109} which assesses each of the *Diagnostic and Statistical Manual of Mental Disorder-V* depression criteria, with the item assessing for suicidality removed. The PHQ-8 has strong psychometric characteristics.¹⁰⁹ This is a CDE proposed by NINDS for measuring depression in people with SCI.

Anxiety will be measured by the **General Anxiety Disorder-7 (GAD-7)**,^{109 110} which assesses anxiety symptoms on a four-point scale and has strong psychometric characteristics. This is a CDE proposed by NINDS for measuring anxiety in people with SCI.

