Aim 1: The number of individuals screened, consented, and randomized per month will be presented, and we will use the CONSORT diagram to summarize the numbers and reasons related to recruitment, follow-up, and dropout. The main feasibility outcomes include recruitment rate, adherence rate and retention rate. a) Recruitment rate: the proportion of eligible people who provide consent (b) Adherence rate the proportion of participants in MM and HE condition who complete a minimum of 60 minutes/week assigned home practice sessions; (c) Retention rate: the proportion of participants in MM and HE condition who meet our criteria for adherence and complete the outcome assessments at baseline, immediate post-intervention and 6-week follow-up. We will summarize these outcomes by arm using frequency, percentage, and 95% confidence intervals. We will inspect these percentages relative to our feasibility targets. Next, we will obtain summary statistics by arm and by study week for the number of sessions completed, the number of days that the participants complete at least 1 session, and total duration of participation (i.e., time spent reviewing the mediation sessions or the TED talk sessions). These data are available in two data sources (i.e., email surveys and app usage data) for the MM Training arm, leading to two sets of variables. We will analyze both sets as well as their differences. For the active control arm (HE), we will summarize adherence data collected via weekly email surveys.

Aim 2: We will first derive item-specific summary statistics for the multiple-choice items in the program evaluation questionnaire by arm. Next, we will use mean, SD, and quartiles to summarize the total score. Qualitative data from the open-ended items on the program evaluation questionnaire will be analyzed using thematic analysis to identify themes of satisfaction and areas for future improvement.

Aim 3: We will calculate the response rate for each measure at baseline, immediate post-intervention, and 6-week follow up to evaluate feasibility and acceptability of collecting these data. For outcomes that are repeatedly measured, we will estimate the mean trajectory by arm using a (generalized) linear mixed model.

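### Does the unstated counting unit of the Aim 3 70%/70% rule let a measure that nobody completes pass as feasible?

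*Combined protocol and SAP*

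**What the plan says.** The Measures section, Aim 3, contains the only numerical criterion for data collection: it "will be determined to be feasible and acceptable if at least 70% of participants complete ≥ 70% of the assessment items". The sentence before it concerns the share of participants in each condition who complete the baseline, post-intervention and 6-week assessments.

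Two other places describe what will be calculated. Aim 3 under Objectives says the team will "calculate the response rate for each measure at baseline, immediate post-intervention, and 6-week follow-up". The Analysis Plan for Aim 3 repeats this ("calculate the response rate for each measure at baseline, immediate post-intervention, and 6-week follow up") and gives the purpose as evaluating whether collecting these data is feasible and acceptable. Neither attaches a threshold to those rates.

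The outcomes are named at three levels of detail. Aim 3 in Measures says "we will collect patient-reported measures of pain, depression, anxiety, mindfulness, and QOL". General Information says "Secondary outcomes include the feasibility of collecting patient-reported outcomes of pain, anxiety, depression, mindfulness, quality of life, stress, fatigue and sleep disturbance". The rest of Measures describes eleven instruments. If participation and completion prove feasible and acceptable, "these measures will serve as primary outcome measures in a subsequent effectiveness trial".

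**The concern.** A rule of the form 70% of people, 70% of items needs a unit for the items, and none is given. The text before the rule uses the word assessment for everything collected at a visit, so a reader may well count items across all instruments. Counted that way, a pass says little about any one instrument: a short form could be missing for every participant and the share of items completed would hardly move.

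This looks important because the result feeds a decision about individual measures, namely whether they can be primary outcomes of the next trial. The pain interview seems the most exposed, since it is done by phone, apart from the web survey, and could be missed as a block. The per-measure response rates would show such a gap but carry no threshold. Retention, defined as those "who meet our criteria for adherence and complete the baseline, immediate post-intervention and 6-week follow-up assessments", does not help either: the Analysis Plan for Aim 1 says "We will inspect these percentages relative to our feasibility targets", but the document gives no retention target. On this view the 70%/70% verdict could stay positive while a key measure failed.

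**Working it through.** **The plan's own figures.** The document computes nothing for the 70%/70% rule. Its precision statement (Statistics, Sample size) reproduces with half-width = 1.96 × √(p(1−p)/n) at n = 30: p = 0.50 gives 17.9% and p = 0.75 gives 15.5%, as stated.

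**Item counts (Measures section).** Stated in words: CPAQ 8, PHQ-8 8, FFMQ-15 15, PAWB-SF 10, PSS-4 4, AAQ-2 7. Read from the instrument name: GAD-7 7, PROMIS Fatigue 4a 4, PROMIS Sleep Disturbance 4a 4. Not given: Brief PCS and the pain interview.

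- Full web battery without Brief PCS: 8+8+7+15+10+4+4+4+7 = 67.
- Eight domains without pain: 8+7+15+10+4+4+4 = 52.
- Five domains without pain: 8+7+15+10 = 40.

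**One measure blank for everyone at one visit.** Share remaining = (T − k)/T, with T items in total and k in the blank measure.

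| Blank measure | Full (67) | Eight domains (52) | Five domains (40) |
|---|---|---|---|
| PAWB-SF (10) | 57/67 = 85.1% | 42/52 = 80.8% | 30/40 = 75.0% |
| FFMQ-15 (15) | 52/67 = 77.6% | 37/52 = 71.2% | 25/40 = 62.5% |

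Adding completed pain or Brief PCS items raises every entry. The five-domain FFMQ-15 entry reaches 70% only when at least 10 completed pain items count: (25+10)/(40+10) = 70%. In general, among four or more measures the shortest holds at most 25% of the items, so it can always be blank under cross-measure counting.

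**Pain interview blank.** With W web items and P pain items, W/(W+P) ≥ 0.70 requires P ≤ 3W/7. The largest P that passes is 28 for W = 67, 34 for W = 80 (Brief PCS assumed to have 13 items), 22 for W = 52 and 17 for W = 40. The document does not give P. As an illustration, the content it names (interference in three areas, plus five attributes for each of three pain problems) makes 3 + 15 = 18 fields. Omission then fails on the five-domain list (40/58 = 69.0%) and passes on the other two.

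**Items pooled over three visits.** A participant who misses one whole visit has 2/3 = 66.7% of items and fails, so ordinary loss of a visit is caught. Partial completion can pass: with baseline completion b, the follow-up completion needed is f = (2.10 − b)/2, that is 55% at b = 100%, 60% at 90% and 65% at 80% (b is assumed).

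**What the plan would show.** The Analysis Plan for Aim 3 gives 11 measures × 3 visits = 33 response rates. A measure that nobody completed at follow-up appears as 0% at that visit, whatever unit is used for the 70%/70% rule.

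**The alternative.** A 70% threshold for each measure at each follow-up visit, among all 60 randomised, requires 42 completers. It would give 11 × 2 = 22 verdicts. At a true completion of 75%, P(X ≤ 41) for X ~ Binomial(60, 0.75) is 0.149. If all 22 had that rate, 22 × 0.149 ≈ 3.3 would be expected to fail by chance. The exact 95% interval at 42/60 is 56.8% to 81.2%; by arm, at 21/30, it is 50.6% to 85.3%.

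**The case for a change.** The strongest case for a change is that the defect lies in the criterion, not in the reporting. A table can show 0% for one measure while the stated rule still returns feasible, and a unit chosen after the data are seen invites a favourable choice. A measure need not be wholly blank, either. Stopping the web survey after PAWB-SF, in the order in which Measures lists the instruments, leaves 48/67 = 71.6% of items and loses PSS-4, both PROMIS forms and AAQ-2. Stating the unit would cost only words.

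Part of this stands. The unit is not written down, nor is it said whether the 70% of participants applies by arm or overall, and cross-measure counting is a possible reading. The rest weakens on inspection. The response rates are planned for the same judgement as the rule, and the Measures text speaks of completing these measures, so a per-measure reading is at least as natural. The item list is less open than it looks: Aim 3 refers to these outcomes, and the text directly after it introduces the full battery as the set whose collection is being tested. The shorter lists are summaries.

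The early-stopping figure depends on a survey order, and on skipping being possible, neither of which can be seen because the survey is an attachment. That the pain interview is the likeliest to be missed is an inference; live administration by staff could equally reduce missing items. The protocol also provides reminders followed by phone calls, 25 dollars for each completed main assessment, repeated testing of the survey with the Community Advisory Board, continuing completeness review, and audits every two weeks for two months and then quarterly.

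**Conclusion.** No change is needed. The counting unit is unstated, and under cross-measure counting the rule is insensitive to the loss of one measure: 77.6% to 94.0% of the 67 countable items remain, depending on which measure is blank (63/67 = 94.0% for a 4-item form). The consequence is small. This is a secondary aim of a descriptive pilot with no between-group testing, and the evidence needed to judge each measure is already planned at every visit. An analyst following the plan would have the measure-level rates at hand when judging feasibility, and could not overlook a measure that nobody completed.

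A formal threshold for each measure is not clearly better. It still has to define how much of a measure counts as complete and whether arms are judged separately, and its 22 verdicts would be imprecise, each with about a 15% chance of failing at a true 75%.

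The conclusion assumes that the planned response rates are reported as described and are read alongside the 70%/70% rule when measures are chosen for the next trial. The item shares rest on lengths stated in the text or read from instrument names; the lengths of Brief PCS and the pain interview are not given.
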